4.4.2 Data Collection and Follow-up for Withdrawn Subjects

Participants who elect to discontinue the hormone protocol or are discontinued for safety reasons will be asked to continue to complete self-report ratings through the end of the proposed study period. However, fMRIs will not be done if participants discontinue the hormone protocol.

5 Study Drug

5.1 Description

Drug	Dosage	Formulation
Conjugated estrogens/bazedoxifene	0.45 milligrams/20 milligrams/day	Oral tablet

5.2 Treatment Regimen

Regimen

Once determined eligible and physically well, participants with perimenopausal depression will receive TSEC (conjugated estrogens/bazedoxifene, 0.45mg/20mg) for 3 weeks. Prior to beginning medication, women will have a basic lab panel and serum pregnancy test, pelvic exam, breast exam, and PAP smear. Participants who can provide record of a pelvic exam and breast exam within the past year and normal pap results within the past three years will be permitted to decline the GYN exam. Women will be seen in the clinic each week during TSEC administration to assess blood levels of estradiol and mood symptoms.

5.3 Method for Assigning Subjects to Treatment Groups

N/A

5.5 Subject Compliance Monitoring

We will monitor participants' compliance with the drug regimen by assaying blood levels of medication collected at weekly study visits. The drug protocol will be reviewed at each study session, and participants who are significantly non-compliant with the study treatment regimen will be discontinued from the study.

5.6 Prior and Concomitant Therapy

Women are required to be medication free to enroll in this study; however, prior medication usage will not preclude participation in the study.

5.7 Packaging

The UNC Investigational Drug Service will receive the active drug from their Pharmacy storeroom. All the Duavee tablets will be provided to participants at study visit 3, in its original blister packaging. Duavee tablets are to be taken once daily. The remaining tablets will be returned to the study team at the conclusion of each subject's participation in the study, and returned to IDS for appropriate disposal.

5.8 Blinding of Study Drug (if applicable)

N/A

5.9 Receiving, Storage, Dispensing and Return

The UNC Investigational Drug Service will receive the study drugs from the UNC Pharmacy Storeroom and will dispense the drug to the PI or research coordinator to deliver to participants. Any unused drug will be returned to the UNC Investigational Drug Service by the PI or research coordinator.

5.9.1 Receipt of Drug Supplies

Upon receipt of the of the study treatment supplies, an inventory will be performed and a drug receipt log filled out and signed by the person accepting the shipment. The designated study staff will count and verify that the shipment contains all the items noted in the shipment inventory. Any damaged or unusable study drug in a given shipment (active drug) will be documented in the study files. The investigator will notify the UNC Pharmacy Storeroom of any damaged or unusable study treatments that were supplied to the Investigational Drug Service.

5.9.2 Storage

Duavee will be stored at 20° to 25° C in a temperature-controlled facility.

5.9.3 Dispensing of Study Drug

Drugs will be dispensed in the manufacturer's blister packaging. Regular study drug reconciliation will be performed to document drug assigned, drug consumed, and drug remaining at each study visit. This reconciliation will be logged on the drug accountability form, and signed and dated by the study team.

5.9.4 Return or Destruction of Study Drug

At the completion of the study, there will be a final reconciliation of drug shipped, drug consumed, and drug remaining. This reconciliation will be logged on the drug reconciliation form, signed and dated. Any discrepancies noted will be investigated, resolved, and documented prior to return or destruction of unused study drug. Drug destroyed on site will be documented in the study files.

6 Study Procedures

The flowchart outlining the procedures at each study visit it attached.

OBGYN Exam

Prior to beginning medication, women will have a basic lab panel and serum pregnancy test, pelvic exam, breast exam, and PAP smear. Participants who can provide record of a pelvic exam and breast exam within the past year and normal pap results within the past three years will be permitted to decline the GYN exam. Results of the exam will be added to the participants' UNC Hospital medical record.

Venipuncture

Participants will undergo venipuncture at 5 study visits. Initial blood tests will include BUN, creatinine, ALT, AST, potassium, chloride, calcium, alkaline phosphatase, and a CBCD to rule out exclusionary health problems. Lab results will be added to participants' medical records. Subsequent venipuncture will be for the purpose of assaying estradiol levels to ensure participant compliance. During the context of COVID-19 venipuncture will be carried out by fully vaccinated study team members in private outdoor settings when possible, such as the subject's backyard.

Drug Administration

Participants will receive their entire supply of Duavee at study visit 3.

Clinical Assessments

The Structured Clinical Interview for DSM-IV-TR Axis-I Disorders (SCID)⁵⁸ and the Schedule for The SCID1 will be administered at baseline to determine study eligibility. The following standard measures will be administered at baseline, both fMRI sessions, and weekly clinic visits:

- The Positive and Negative Affect Schedule⁵⁹ is a 20-item questionnaire that measures both positive affect (PA) and negative affect (NA) and is sensitive to subtle changes in affect over time.

- The Hamilton Rating Scale for Depression (HRSD)⁶⁰ is a 21-item researcher-rated standardized scale that assesses depressive symptoms and is widely used as a measure of symptom change over time.
- The Inventory of Depression and Anxiety Symptoms (IDAS)⁶¹ is a 64-item self-report questionnaire that comprehensively assesses anxiety and depression symptoms on 10 subscales. The IDAS has excellent psychometric properties and has been validated for assessing reproductive mood disorders.
- The Mood and Anxiety Symptom Questionnaire – Anhedonic Depression Subscale (MASQ-AD)⁶² is a 22-item scale that assesses anhedonia (i.e., loss of interest and low positive affect). MASQ-AD scores have been associated with blunted striatal response to reward in previous studies of patients with depression⁶³.
- The Greene Climacteric Scale (GCS)⁶⁴ is a 21-item scale that is the gold-standard measure of four domains of climacteric symptoms: vasomotor, somatic, anxiety, and depression.
- The Pittsburgh Sleep Quality Index (PSQI)⁶⁵ is a 9-item questionnaire that measures the quality and sleep patterns in older adults. *This measure will only be administered at the two fMRI sessions.
- The Hormone History Questionnaire is a 19-item inventory that assesses women's mental and physical health and was created for the purpose of this study.
- The Trauma History Questionnaire¹⁴ is a 24-item measure that examines participant's experiences with potentially serious or traumatic life events.

While the SCID and HAM-D are researcher administered, the other measures will be collected through self-report questionnaires using *Qualtrics* or paper and pencil questionnaires.

Despite the use of exclusion criteria designed to reduce risk to participants, depressive symptoms are monitored closely. Any subject who develops severe depressive symptoms (e.g., suicidal ideation) will be discontinued from the study and offered treatment, including inpatient hospitalization.

FMRI Tasks

The following task will be included in each of the two fMRI sessions:

The Monetary Incentive Delay (MID) Task⁶⁶ engages the reward circuitry during monetary incentive anticipation and outcomes. Each of two MID runs consists of 90 6-second trials during which subjects are presented with one of nine cue shapes, a fixation crosshair (for a variable duration), the target, and performance (win/loss/neutral) feedback. The cue indicates whether it is an incentive (gain, loss) or non-incentive trial. During incentive trials, participants can either gain or lose money by pressing a button during target presentation. Task difficulty is based on participant reaction times. This task elicits reliable frontostriatal dysregulation in people with remitted MDD⁶⁷. Resting state scans will also be conducted at the beginning and end of each session.

The Hariri Emotional Faces Task is an emotional face-matching task that engages neuronal regions implicated in emotional processing, including the amygdala and dorsomedial PFC. This block design paradigm consists of 4 blocks of a perceptual face-processing task interleaved with 5 blocks of a sensorimotor control task. Participants are presented with a target stimulus and asked to select one of 2 images, presented on the low half of the screen, which match the target. Each face-processing block consists of fear and anger sub-blocks. During the sensorimotor control blocks, subjects view a trio of simple geometric shapes.

FMRI Data Acquisition and Image Processing. Scanning was initially performed using a Siemens Magnetom 3T TIM Trio scanner. In July 2016, the scanner was upgraded to a Siemens 3T Prisma, and as such, all scanning will be performed on the Prisma system going forward. Scanning parameters on the Prisma were set to be identical to the Trio in order to minimize the effects of scanner on the data.

High-resolution, T1-weighted anatomical images will be acquired using an MPRAGE sequence. Whole-brain functional images will be acquired using a single-shot, gradient recalled echoplanar pulse sequence sensitive to blood-oxygen-level-dependent (BOLD) contrast. Each of 2 runs will consist of the acquisition of 195 successive brain volumes. FMRI image preprocessing, processing, and analysis will be conducted using FSL and custom MATLAB scripts. FMRI analyses will include an event-related BOLD response analysis within *a priori* structurally defined frontostriatal regions of interest (ROIs). Contrasts of interest will include win versus non-win outcomes⁹, although the anticipation of wins will also be explored.

Pizzagalli's Probabilistic Reward Task (PRT)¹² will be conducted outside of the scanner. This task allows us to test the additional hypothesis that perimenopausal depression is characterized by blunted reward learning. During this task, correct identifications of two ambiguous stimuli are differentially rewarded. The task will consist of 1 00 trials, in 1 block. Each trial starts with the presentation of a fixation cross for 500 msec followed by a mouthless face. After a delay of 500 msec, either a short mouth (11.5 mm) or a long mouth (13 mm) is presented for 100 msec. Participants will be asked to identify which type of mouth was presented. For each block, the long and short mouths are presented equally often in a pseudorandomized sequence and 40 correct trials are followed by reward feedback immediately after the correct response. An asymmetrical reinforcer ratio will be used in this task, such that for half of the participants, correct identification of the short mouth will be associated with three times more positive feedback (30 of 40) than correct identification of the long mouth (10 of 40). For the other half of the participants, the contingencies will be reversed.

7 Statistical Plan

7.1 Sample Size Determination

The researchers will have 80% power to detect a large effect size (.7) in 20 women. Our recently completed study of the effects of transdermal estradiol on mood symptoms in the same population showed a reduction in depressive symptoms with the PM-MDD group from pre-treatment to post-treatment ($t=4.3$, $p<0.001$ Cohen's $d=1.15$). We anticipate the TSEC (the active ingredient of which is estrogen) to have similar effects on mood symptoms, and thus, the sample size of 20 is a conservative estimate of the number of subjects we will need to detect a statistically significant effect.

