7.2 Statistical Methods

Aim 1: Determine the extent to which TSEC reduces anhedonia and other depressive symptoms in PM-MDD. Anhedonia and other depressive symptoms will be assessed at baseline and following 3 weeks of TSEC administration. Null hypothesis (H0): TSEC has no salutary effect on depression. Alternative hypothesis (H1): TSEC reduces depression as evidenced by 1) a statistically significant decrease in average MASQ Anhedonia scale score following 3 weeks of treatment, and 2) a clinically significant increase of 1 SD in MASQ Anhedonia scale score. We will test this hypothesis using a paired t-test of MASQ Anhedonia scores at visit 1 (pre-treatment) and visit 6 (post-treatment).

Aim 2 (Exploratory): Quantify the effect of TSEC on the neural reward system in PM-MDD. We will use fMRI at baseline and following TSEC treatment in PM-MDD to probe frontostriatal reward circuitry. We also will compare the effects of TSEC and ERT in PM-MDD. Null hypothesis (H0): TSEC has no meaningful effect on activity of the neural reward circuit in response to rewards. Alternative hypothesis (H1): TSEC reduces increases neural responsiveness to reward in the frontostriatal reward circuitry as evidenced by increased activation of the caudate, putamen, and nucleus accumbens in PM-MDD in response to reward following TSEC administration (compared with baseline). We will test this hypothesis using a paired t-test to compare activity in 3 regions of interest (ROIs)—caudate, putamen, and nucleus accumbens—at the pretreatment and posttreatment scans.

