We will have 80% power to detect a large effect size (.7) in 20 women. Our recently completed study of the effects of transdermal estradiol on mood symptoms in the same population showed a reduction in depressive symptoms with the PM-MDD group from pre-treatment to post-treatment ($t=4.3$, $p<0.001$ Cohen's $d=1.15$). We anticipate the TSEC (the active ingredient of which is estrogen) to have similar effects on mood symptoms, and thus, the sample size of 20 is a conservative estimate of the number of subject we will need to detect a statistically significant effect.

B. Safety and study progress reviews

1. The research coordinator will evaluate the study subjects at appropriate intervals and assess laboratory data and clinical signs for potential adverse events. The research coordinator will assist the PI with gathering information to help the PI determine classification and causality. The research coordinator will also observe and document all adverse events, act on the PI's recommendation, and maintain follow-up until reconciliation.
2. The principal investigator and [name] will review the adverse events, immediately after they occur, with follow-up resolution. The principal investigator and [name] will evaluate individual and cumulative participant data when making recommendations regarding the safe continuation of the study. The principal investigator will be notified within 24 hours of an adverse event.
3. Specific responsibilities of the principal investigator include:
 - a. Review the research protocol, informed consent documents, and plans for data safety and monitoring;
 - b. Evaluate the progress of the trial, including periodic assessments of data quality and timeliness, participant recruitment, accrual and retention, participant risk versus benefit, performance of the trial site, and other factors that can affect study outcome;
 - c. Consider factors external to the study when relevant information becomes available, such as scientific or therapeutic developments that may have an impact on the safety of the participants or the ethics of the trial;
 - d. Protect the safety of the study participants;
 - e. Report on the safety and progress of the trial;
 - f. Make recommendations to the UNC-CH IRB, and, if required to the Food and Drug Administration (FDA) concerning continuation, termination, or other modifications of the trial based on the observed beneficial or adverse effects of the treatment under study;

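### The stated 80% power is for the paired t-test alone, but H1 for Aim 1 also asks for a 1-SD change that has no power figure and is printed in the wrong direction

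*Combined protocol and SAP*

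**What the plan says.** Section 7.1 gives the power statement: "The researchers will have 80% power to detect a large effect size (.7) in 20 women". It then cites the group's completed transdermal estradiol study (t = 4.3, Cohen's d = 1.15 on depressive symptoms) and adds: "We anticipate the TSEC (the active ingredient of which is estrogen) to have similar effects on mood symptoms". On that basis it calls "the sample size of 20 is a conservative estimate of the number of subjects we will need to detect a statistically significant effect". Appendix A III.A repeats the statement: "We will have 80% power to detect a large effect size (.7) in 20 women".

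H1 for Aim 1 appears in Section 2, Section 7.2 and the statistical analysis strategy in Appendix A. It has two numbered parts joined by *and*:

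- Part 1: "a statistically significant decrease in average MASQ Anhedonia scale score following 3 weeks of treatment".
- Part 2: "a clinically significant increase of 1 SD in MASQ Anhedonia scale score".

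The only test named is a paired t-test of visit 1 against visit 6. The Statistical Methodology row of the Study Summary names that test and does not mention the 1-SD mark. No section says which SD is meant, whether the mark applies to the group mean or to each woman, or how part 2 is to be judged.

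**The concern.** Aim 1 is the only aim not labelled exploratory, so its H1 decides what the trial can claim. The power statement answers one question (will the mean change be significant?) while H1 asks two. The effect used for the power statement, 0.7, lies below the 1-SD mark that H1 calls clinically significant. Part 2 is therefore the harder condition, and it is the one with no power figure.

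At a true effect of 0.7 the most likely result is a significant change smaller than 1 SD. Under H1 taken strictly, that result fails. Under the sentence naming the t-test, it succeeds. The plan does not say which governs, so the choice could be made after the data are seen.

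The direction printed in part 2 adds to this: an increase in the anhedonia score would be a worsening, and it contradicts part 1.

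**Working it through.** **Inputs.** From the plan: n = 20, single group, paired test, effect 0.7, stated power 80%, anticipated effect similar to d = 1.15 (Section 7.1); the two parts of H1 (Section 7.2). My assumptions: two-sided alpha 0.05 (not stated), 0.7 measured in SDs of the paired change (standardiser not named), all 20 women analysed, normal data, and part 2 read as a 1-SD *improvement in the group mean*.

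The 1.15 is consistent with the SD-of-change scale: for a paired test d = t/√n, so n = (4.3/1.15)² = 13.98, close to a whole number. This is an inference, because the plan does not give that study's sample size.

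**Step 1: reproduce the stated power.** Noncentral t, df = 19, noncentrality 0.7 × √20 = 3.13, critical value 2.093. Power = 84.4%. The effect detectable with 80% power at n = 20 is 0.66, and the smallest n giving 80% at 0.7 is 19. The stated 80% is slightly conservative for the t-test alone.

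**Step 2: which part is harder?** The t-test is significant from an observed change of 2.093/√20 = 0.468 SDs of change. An observed change of 1 SD of change gives t = √20 = 4.47. Anything that meets part 2 on this scale also meets part 1, so the joint chance is the chance of part 2.

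**Step 3: chance of both parts, mark in SDs of change.** With the SD treated as fixed: P(Z ≥ (1 − d) × √20). At d = 0.7 this is P(Z ≥ 1.342) = 9.0%. At d = 1.15 it is P(Z ≥ −0.671) = 74.9%. With the sample SD: P(t ≥ 4.47) under a noncentral t with noncentrality d × √20.

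| True effect | t-test alone | Both parts, fixed SD | Both parts, sample SD |
|---|---|---|---|
| 0.7 | 84.4% | 9.0% | 14.9% |
| 1.0 | 98.9% | 50.0% | 52.1% |
| 1.15 | 99.8% | 74.9% | 72.4% |

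At 0.7, the chance of a significant result below 1 SD is 84.4 − 14.9 = 69.5% (sample SD) or 84.4 − 9.0 = 75.4% (fixed SD). A joint chance of 80% needs a true effect of about 1.2 SDs of change.

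**Step 4: mark in baseline SDs.** With equal SDs before and after and pre-post correlation r, the SD of change is √(2(1 − r)) baseline SDs. The true change is d × √(2(1 − r)) and its standard error is √(2(1 − r)/20). For r = 0.3 and d = 0.7: true change 0.828, standard error 0.265, P(Z ≥ 0.172/0.265) = 26%. The plan gives no r. Fixed-SD results, with those using the sample baseline SD in brackets:

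| r | Both parts, d = 0.7 | Both parts, d = 1.15 |
|---|---|---|
| 0 | 49% (51%) | 98% (96%) |
| 0.3 | 26% (31%) | 91% (89%) |
| 0.5 | 9% (15%) | 75% (72%) |
| 0.7 | 0.4% (2.8%) | 26% (34%) |

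Simulation (400,000 trials per row) gave the bracketed values and agrees with the formula for the others. If 0.7 is itself in baseline SDs, the joint chance against a baseline-SD mark is 17-21% at r = 0, 9-15% at r = 0.5 and 4-11% at r = 0.7. If 0.7 is in baseline SDs but the mark is in SDs of change, it runs from 4% at r = 0 to 67% at r = 0.8 (sample SD).

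**Step 5: per-woman reading.** On the SD-of-change scale the expected share improving by at least 1 SD is P(Z ≥ 0.3) = 38% at 0.7. The plan sets no required share, so no power can be computed.

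**The case against.** **0.7 is not the effect the plan expects.** A reader might infer that the trial has only a 9-15% chance of success under its own planning assumption. The documents do not support that. Section 7.1 uses 0.7 as a detectable effect and anticipates something close to 1.15, where the joint chance is 72-75% on the SD-of-change scale, not far below 80%. With a baseline SD and a low correlation it exceeds 80%. This objection stands, so both effects must be shown. But 0.7 cannot be set aside: the 1.15 comes from a different drug and from depressive symptoms generally, and Section 1.1 itself cautions against assuming that estrogen's antidepressant effect carries over when bazedoxifene is present.

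**Section 7.1 speaks only of significance.** This is correct. A reader might infer that the 80% is miscalculated; it is not. Nor does Section 7.1 say that H1 as a whole has 80% power. What is missing is any figure for the condition that H1 adds.

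**The 1-SD mark may be only an interpretive benchmark.** The t-test is the only named procedure, the Study Summary omits the mark, and Section 1.1 describes the study as a source of pilot data for a larger randomised trial. That reading is possible. The numbered parts joined by *and*, repeated in three places, point the other way, and nothing in the text settles it.

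**As printed, both parts cannot hold for the same mean.** A reader might infer that the trial can never succeed. That presses what looks like a wording slip too far: a clinically significant increase in anhedonia is not a sensible sign of benefit. Still, the percentages above apply to a corrected H1, not to the printed one.

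**Conclusion.** The point holds as a mismatch between sections. The 80% belongs to the paired t-test, while H1 for Aim 1 adds a 1-SD condition with no power, no defined SD, no stated level and a contradictory direction.

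The size is conditional. For a 1-SD improvement in the group mean on the SD-of-change scale, the joint chance is about 9-15% at 0.7 and 72-75% at 1.15. The two-sided alpha of 0.05 affects the t-test figures but not these joint ones, because part 2 is the stricter condition. With a baseline SD and effects in SDs of change, the fixed-SD joint chance at 0.7 runs from 49% (r = 0) to 0.4% (r = 0.7); at 1.15 it runs from 91% (r = 0.3) to 26% (r = 0.7). On every group-mean reading tested here the joint chance at 0.7 is below the stated 80%, but no single percentage can be called the power for H1 until part 2 is defined.

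**What to change.** 1. In Section 2, Section 7.2 and the analysis strategy in Appendix A, change part 2 to a decrease (improvement) of 1 SD. Name the SD (baseline or change) and say whether it applies to the group mean or to each woman.

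2. Preferably, decide H1 on the paired t-test alone. In Section 7.1 and Appendix A III.A, label the 80% as power for that test, and state alpha, sidedness and the standardiser of 0.7. Report the 1-SD mark descriptively: mean change with 95% CI, and the share of women improving by 1 SD or more.

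3. If both parts remain required, state the joint power at both 0.7 and 1.15 in Section 7.1 and Appendix A III.A, with the assumed pre-post correlation if the baseline SD is chosen. Say that a significant change below 1 SD does not meet H1. A per-woman criterion would also need a required share.

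The cost is wording only, with no added participants, visits or tests. If both parts are kept, the stated power becomes less favourable on most readings.
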